Document Number:	c31693972-02					
EudraCT No. EU Trial No.	2019-003853-27						
Boehringer Ingelheim (BI) Trial No.	1405-0008						
BI Investigational Medicinal Product(s)	BI 1323495						
Title	Safety, tolerability, pharmacokinet different oral doses of BI 1323495 with non-cystic fibrosis bronchiect blind, placebo-controlled, parallel	ics, and pharmacodynamics of versus placebo in patients asis (randomised, double- group trial)					
Lay Title	A study in patients with non-cystic fibrosis bronchiectasis to test how well different doses of BI 1323495 are tolerated and how BI 1323495 affects biomarkers of inflammation						
Clinical Phase	Phase Ic						
Clinical Trial Leader	Phone: Fax:						
Coordinating Investigator							
Version and Date	Version: 2.0	Date: 22 Apr 2021					
	Page 1 of 111						

Page 2 of 111

Proprietary confidential information © 2021 Boehringer Ingelheim International GmbH or one or more of its affiliated companies

Proprietary confidential information.

© 2021 Boehringer Ingelheim International GmbH or one or more of its affiliated companies. All rights reserved. This document may not - in full or in part - be passed on, reproduced, published or otherwise used without prior written permission.

CLINICAL TRIAL PROTOCOL SYNOPSIS

Company name	Boehringer Ingelheim
Protocol date	17 Sep 2020
Revision date	22 Apr 2021
BI trial number	1405-0008
Title of trial	Safety, tolerability, pharmacokinetics, and pharmacodynamics of different multiple oral doses of BI 1323495 versus placebo in patients with non-cystic fibrosis bronchiectasis (randomised, double-blind, placebo-controlled, parallel group trial)
Coordinating	
Investigator	
Trial site(s)	Multi-centre trial conducted in 2 countries
Clinical phase	Phase Ic
Trial rationale	After establishing safety and tolerability in healthy volunteers, the trial is intended to confirm the safety and tolerability of multiple doses of BI 1323495 in a population of patients with non-cystic fibrosis bronchiectasis (nCFB), and to assess the inhibition of neutrophil elastase (NE) in blood and sputum.
Trial objective(s)	The main objectives of this trial are to compare safety and tolerability of different doses of BI 1323495 with placebo and to assess pharmacodynamics of BI 1323495 in sputum and in blood as well as early signs of clinical efficacy of BI 1323495 in patients with nCFB.
Trial endpoints	 Primary endpoint: The safety and tolerability of BI 1323495 will be assessed based on the occurrence of drug-related adverse events. Secondary endpoints: Change from baseline to week 12 in absolute NE activity in sputum Change from baseline to week 12 in neutrophil cell count in sputum Change from baseline to week 12 in NE activity in whole blood after stimulation with zymosan, normalized to neutrophil cell counts Change from baseline to week 12 in post-bronchodilator forced expiratory volume in one second (FEV1)
Trial design	Multicentre, randomised, double-blind (patient and investigator blinded), placebo-controlled, parallel group trial over 12 weeks treatment
Total number of patients randomised	36 patients in Parts A and B
Number of patients on each treatment	 9 patients on placebo (in total in Parts A and B) 9 patients on BI 1323495 30mg bid in Part A 18 patients on BI 1323495 150 mg qd in Part B
Diagnosis	Proven and documented diagnosis of bronchiectasis not related to cystic fibrosis
Main in- and exclusion	• 18 years to 80 years (inclusive), male and female (not of

B1693972-02Clinical Trial ProtocolPage 4 of 111Proprietary confidential information © 2021 Boehringer Ingelheim International GmbH or one or more of its affiliated companies

criteria	childbearing potential) subjects
	Clinical history consistent with nCFB and proven and
	documented diagnosis of bronchiectasis by CT and dilated
	airways compatible with bronchiectasis at initial diagnosis
	• Regular daily sputum producers with a history of chronic
	expectoration who are able to provide a valid sputum sample
	during screening (SCR)
	• Sputum neutrophil elastase positive based on point-of-care test
	(NEATstik [®] score ≥ 6 or equivalent) assessment at baseline
	• UDP-glucuronosyltransferase 2B17 (UGT2B17) extensive
	metabolizer (EM) (genotypes *1/*1 or *1/*2)
	• Stable regimen of standard nCFB treatment allowed
	No concomitant diagnosis of pulmonary disease other than
	bronchiectasis, chronic obstructive pulmonary disease (COPD),
	or asthma
Test product(s)	BI 1323495 film-coated tablets (tablet strengths 10 and 50 mg)
dose	In Part A: 60 mg daily (30 mg bid). In Part B: 150 mg qd
mode of administration	Oral (p.o.) within 30 minutes of a meal containing a fat component
Comparator product(s)	Matching placebo
dose	Not applicable
mode of administration	Oral (p.o.) within 30 minutes of a meal containing a fat component
Duration of treatment	84 days: In Part A, 83 days twice daily (bid) and single dose on day
	84; in Part B, 84 days once daily (qd)
Statistical methods	The primary and secondary endpoints will be evaluated using
	descriptive statistics.

Page 5 of 111

Proprietary confidential information © 2021 Boehringer Ingelheim International GmbH or one or more of its affiliated companies

MAIN FLOW CHART

Trial Periods	Screening ¹	Ru (Bas B	n-in eline - SL)	Randomised Treatment Period							Follow- up (FUP)		
Visit ²	1	2a BSL	2b BSL	3 ³	4 ¹⁵	5	6 PK Day	7 ¹⁶	8	9a	9b	10 EoT / early EoT ⁴	11 FUP / EoS
Week	-4	-1		0	1	2	4	6	8	11		12	14
Day	-27	-6	-2	1	8	15	29	43	57	78	82	84	98
Time window for visits (days)	+14	+2	+1	±0	±3	±3	±3	±3	±3	+3	+1	+3	±4
Informed consent	X												
Demographics	Х												
Medical history including Smoking status and alcohol history	x												
Testing for UGT2B17 genotype	X												
Physical examination	Х			Х			Х					Х	X
Height (only at V1)/ body weight	X			X			X					X	X
Vital signs: pulse rate (PR), blood pressure (BP), aural body temperature	X			X		X	X		X			X	x
Laboratory tests (blood/urine)	X ¹³			X		X	X	X	X			X	X
12-Lead Electrocardiogram (ECG) (single ECG, may be repeated by investigator judgement)	Х			X		x	X		x			X	
Pregnancy test in women (serum S / urine U)	X (S)			X (U) ⁵					X (U) ⁵			X (U) ⁵	
Concomitant therapy	X	X	X	X	X	X	X	X	X	X	X	X	X
Review of in-/exclusion criteria	X	X	X	X									
Randomisation				Х									

Boehringer Ingelheim BI Trial No.: 1405-0008 c31693972-02

Clinical Trial Protocol

Page 6 of 111

Proprietary confidential information © 2021 Boehringer Ingelheim International GmbH or one or more of its affiliated companies

Trial Periods	Screening ¹	Ru (Bas B	in-in eline - SL)				Randomis	ed Treat	ment Peri	iod			Follow- up (FUP)
Visit ²	1	2a BSL	2b BSL	3 ³	4 ¹⁵	5	6 PK Day	7 ¹⁶	8	9a	9b	10 EoT / early EoT ⁴	11 FUP / EoS
IRT call/notification ¹²	X			X		X	X		X			X	
Administer trial drugs at site ⁶				Х			X						
Dispense trial drugs for home ⁶				Х		X	Х		Х				
PK blood sampling (see Sample and Assessment Flow Chart)				X		X	X					X	
Lung questionnaires (QoL-B; SGRQ; CASA-Q)			X						X			X	
Sputum (collected at site) ^{7, 14}	X ¹⁷	Χ	Χ	Χ		X	X		X	X	X	X	X
24h Sputum (collected at home) ⁸				X			X					X	
Murray sputum colour chart			Χ	X								Х	
NEATstik [®] (NE determination)		Χ	Χ									X	
Blood sample for biomarkers, pharmacodynamic (PD)			X	Х		X	X		X			X	X
Zymosan stimulation in whole blood			X	X		X	X		X			X	X
Cotinine test			Χ	Х		X	X		Χ			X	X
Serum banking sample (optional) ⁹			X	X		X	X		X			X	X
Urine banking sample (otional) ⁹			X										
Pulmonary Function Test (PFT) ¹⁰	X		X			X			X			X	X
All AEs/SAEs/AESIs ¹¹	X	Χ	Χ	Χ	Χ	X	X	X	Χ	Χ	Χ	X	X
Compliance check (medication)						X	X		X			X	
Completion of patient participation													X

Boehringer Ingelheim		22 Apr 2021
BI Trial No.: 1405-0008		
c31693972-02	Clinical Trial Protocol	Page 7 of 111
	Proprietary confidential information © 2021 Boehringer Ingelheim International GmbH or one or more of its affiliated companies	
1. Informed consent need	s to be signed before any procedure related to this trial is performed (before or at Visit 1).	

- 2. Timing of sampling and assessments: see Sample and Assessment Flow Chart.
- 3. Day of Randomisation / Day of first intake of randomised medication.
- 4. Patients who discontinue trial treatment prematurely should undergo an early End of Treatment (EoT) visit as soon as possible (study procedures will be the same as for Visit 10 (EoT) except no treatment will be administered). Follow up Visit (End of Study (EoS)) will be 14 days +/- 4 days thereafter.
- 5. Serum pregnancy test is to be performed if urine test positive and no Investigational Medicinal Product (IMP) to be given until negative result confirmed.
- 6. Following first drug administration in Part A, evening and morning dose should be taken with a 12 h time interval (e.g. 20:00 h and 08:00 h) approximately at the same time each day during the treatment phase, within a time window of +/- 1 hour. In Part B, the once-daily dose should be taken approximately at the same time each morning during the treatment phase. Drug should be taken 15-30 min after food intake including a fat component (like yogurt, milk, cheese or sausage). As an exemption, at Visit 3 and Visit 6, drug administration will happen at the site outside the normal schedule. Patients will then go back to their usual evening/morning interval (Part A) or once-daily interval (Part B), respectively. At Visit 3, patient will receive a reserve kit in case medication gets lost or the patients comes back to the next visit after more than 2 weeks. The morning drug administration date/time is collected on the eCRF for all Visits 3 to 10 (except Visit 4).
- 7.
- 8. Sputum containers for 24h sputum collection will be provided to the patient at Visit 2b, Visit 5 and Visit 9b.
- 9. Collection of biobanking samples is optional and requires a separate informed consent form (ICF).
- 10. If treated with bronchodilators, wash-out of 24 hours for qd long acting, 12 hours for bid long acting, and 8 hours for short acting bronchodilators should be observed before pulmonary function tests. Screening PFT would also be accepted without wash-out in case consent was only signed on the same day.
- 11. After the EoS visit (=individual patient's end of the trial) the investigator should report only any cancers of new histology and relapse of existing cancer, trial treatment related adverse events (AEs), serious adverse events (SAEs) and trial treatment related adverse events of special interest (AESIs) of which the investigator may become aware of and only via the BI SAE form, please see Section 5.2.6.2.1.
- 12. Screening has to be registered in the Interactive Response Technology (IRT) at time of informed consent to trigger initial medication supply to the site.
- 13. Polymerase Chain Reaction (PCR) Test on SARS-CoV-2 to be performed only at Screening.
- 14. Left over volume of sputum samples may be used for optional biobanking see Section 5.5.
- 15. Visit 4 will be conducted as a phone call with the patient.
- 16. Visit 7 will be conducted as a phone call and blood for safety lab will be collected at a local lab or by a flying nurse.
- 17. Sputum collection for check of inclusion criterion #7

Proprietary confidential information © 2021 Boehringer Ingelheim International GmbH or one or more of its affiliated companies

SAMPLE AND ASSESSMENT FLOW CHART

Visit	Day Window	Planned time (relative to last drug administration [h:min] ¹	Approximate clock time of actual day [h:min] ¹	Event and comment	Safety laboratory	12-lead ECG ² , Vital signs	${ m PK}_{ m blood}{}^3$	Blood for PD readouts	Biobanking sample	Lung questionnaires ⁴	Sputum collection ⁵	Pulmonary function test ⁶	24 h Sputum	Murray colour chart	NEATstik®
			08:00	Screening visit											
V 1	-27		08:30	Safety	X7	Х									L
• -	+14		09:00	Sputum collection for inclusion check							Х			jł	L
			11:00	Pulmonary function								Х		j	 
V2a	-6 +2		09:00	Sputum collection incl NEATstik®							Х				Х
			08:00	Blood PD, serum and urine banking ⁸				Х	Х						
Wah	-2		08:30	Questionnaires						Х					
V 2.0	+1		09:00	Sputum collection incl Murray chart and NEATstik®							Х			Х	Х
			11:00	Pulmonary function								Х			
		-02:30	08:00	Hand over of 24h sputum collected at home, safety, baseline PK and blood PD, serum banking ⁸	X ⁷	Х	Х	Х	х				Х		
1/2	1	-02:00	08:30	Sputum collection incl. Murray chart							Х			Х	
V 3	1	00:00	10:30	First drug administration											
		06:00	16:30	Safety	Х	Х									
		06:30	17:00	Discharge from trial site ⁹ ; at home: Follow daily drug posology ¹⁰											
	15		08:00	Drug intake at home. At site: safety, blood PD, PK, serum banking ⁸	Х	Х	Х	Х	Х						
V5	+3		09:00	Sputum							Х				
			11:00	Pulmonary function								Х			

22 Apr 2021

Boehringer Ingelheim BI Trial No.: 1405-0008 c31693972-02

Clinical Trial Protocol

Page 9 of 111

Proprietary confidential information © 2021 Boehringer Ingelheim International GmbH or one or more of its affiliated companies

Visit	Day Window	Planned time (relative to last drug administration [h:min] ¹	Approximate clock time of actual day [h:min] ¹	Event and comment	Safety laboratory	12-lead ECG ² , Vital signs	$\mathbf{PK}_{blood}{}^3$	Blood for PD readouts	Biobanking sample	Lung questionnaires ⁴	Sputum collection ⁵	Pulmonary function test ⁶	24 h Sputum	Murray colour chart	NEATstik®
		-1:30	08:00	No drug intake at home . At site: safety, trough PK, blood PD, hand over of 24h sputum collected at home, serum banking ⁸	х	Х	Х	Х	Х				Х		
		-0:30	08:30	Sputum collection							Х				
	20	0:00	10:30	Drug administration at site											
V6	29 +3	1:00	11:30	РК			Х								
	±5	2:00	12:30	РК			Х								
		4:00	14:30	РК			Х								
		6:00	16:30	Safety, PK, Blood PD	Х	Х	Х	Х							
			17:00	Discharge from trial site ⁹ ; at home: Follow daily drug posology ¹⁰											
V 7	43 ±3		8:00	Safety blood collected at a local lab or by a flying nurse	Х										
			08:00	Safety, blood PD, serum banking ⁸	Х	Х		Х	Х						
1/0	57		08:30	Questionnaires						Х					
vo	±3		09:00	Sputum collection							Х				
			11:00	Pulmonary function								Х			
V9a	78 +3		08:00	Sputum collection							Х				
V9b	82 +1		08:00	Sputum collection							X				
V10	84 +5		08:00	Last drug administration at home; EoT site visit: Hand over of 24h sputum collected at home, safety, blood PD, PK, serum banking ⁸	Х	X	X	X	X				X		
			08:30	Questionnaires						Х					
			09:00	Sputum collection incl. Murray chart, NEATstik®							Х			Х	Х

Page 10 of 111

Proprietary confidential information © 2021 Boehringer Ingelheim International GmbH or one or more of its affiliated companies

Visit	Day Window	Planned time (relative to last drug administration [h:min] ¹	Approximate clock time of actual day [h:min] ¹	Event and comment	Safety laboratory	12-lead ECG ² , Vital signs	$\mathbf{PK}_{\mathrm{blood}}^{3}$	Blood for PD readouts	Biobanking sample	Lung questionnaires ⁴	Sputum collection ⁵	Pulmonary function test ⁶	24 h Sputum	Murray colour chart	NEATstik®
			11:00	Pulmonary function								Х			
V11	98		08:30	Safety, blood PD, serum banking ⁸	Х	X ¹¹		Х	Х						
	±5		09:00	Sputum collection							Х				
			11:00	Pulmonary function								Х			

- 1. The time is approximate; a deviation from the scheduled time of the day of \pm 120 minutes is acceptable. The relative time deviations from time of administration should be kept as minimal as possible and should be below \pm 15 minutes for PK measurements. The exact time of sample collection should be collected in electronic Case Report Form (eCRF).
- 2. ECG recordings are performed as single ECGs (no central ECG lab). The ECG recording may be repeated by investigator judgment for medical or quality reasons.
- 3. Sampling times and periods may be adapted based on information obtained during the trial (e.g. preliminary PK data) including addition of blood samples and visits as long as the total blood volume taken does not exceed 500 mL per subject.
- 4. Self-reported outcome questionnaires include: Quality of Life Questionnaire-Bronchiectasis, QOL-B; St. George's Respiratory Questionnaire, SGRQ; Cough and sputum assessment questionnaire, CASA-Q. Questionnaires should be done in a quiet place prior to the lung-related visit procedures.
- 5. Sputum collection should occur during a 2h timeframe with active breathing techniques. Study nurse / physiotherapist needs to be available to support patient in performing active cycle of breathing technique in case of difficulties producing sputum. Next step will be Oscillating Positive Expiratory Pressure (OPEP), if despite breathing technique still no sputum is being produced. Patients who produce an adequate sputum sample do not have to undergo these supportive measures. In case no adequate sputum sample is produced spontaneously, induction of sputum with isotonic, or subsequently hypertonic saline is mandatory. If sputum samples do not meet the quality criteria as directly assessed at the site, re-sampling at the next day is generally possible.
- 6. If treated with bronchodilators, wash-out of 24 hours for qd long acting, 12 hours for bid long acting, and 8 hours for short acting bronchodilators should be observed before pulmonary function tests.
- 7. Including urine drug screening and alcohol breath test
- 8. Collection of biobanking samples is optional. Participating patients are required to give informed consent specifically for biobanking. Samples will be stored at a biobanking facility for future research.

22 Apr 2021

Boehringer Ingelheim		22 Apr 2021
BI Trial No.: 1405-0008		
c31693972-02	Clinical Trial Protocol	Page 11 of 111
	Proprietary confidential information © 2021 Boehringer Ingelheim International GmbH or one or more of its affiliated companies	

9. Discharge is not mandatory and always at discretion of the investigator. Patient in-house stay may be extended at any time if deemed clinically necessary. The subjects are only allowed to leave the trial site after formal assessment and confirmation of their fitness by the investigator or designee.

10. Following first drug administration in Part A, evening and morning dose should be taken with a 12 h time interval (e.g. 20:00 h and 08:00 h) approximately at the same time each day during the treatment phase, within a time window of +/- 1 hour. In Part B, the once-daily dose should be taken approximately at the same time each morning during the treatment phase. Drug should be taken 15-30 min after food intake including a fat component (like yogurt, milk, cheese or sausage). As an exemption, at Visit 3 and Visit 6, drug administration will happen at the site outside the normal schedule. Patients will then go back to their usual evening/morning interval (Part A) or once-daily interval (Part B), respectively.

11. At V11, only Vital Signs need to be assessed

Page 12 of 111

Proprietary confidential information © 2021 Boehringer Ingelheim International GmbH or one or more of its affiliated companies

TABLE OF CONTENTS

TITLE F	PAGE	1
CLINIC	CAL TRIAL PROTOCOL SYNOPSIS	3
MAIN F	LOW CHART	5
SAMPL	E AND ASSESSMENT FLOW CHART	8
TABLE	OF CONTENTS	12
ABBRE	VIATIONS	16
1.	INTRODUCTION	21
1.1	MEDICAL BACKGROUND	
1.2	DRUG PROFILE	21
1.2.1	Mode of action	
1.2.2	Data from non-clinical and toxicology studies	
1.2.2.1	Non-clinical pharmacology	
1.2.2.2	Non-clinical pharmacokinetics	23
1.2.2.3	Drug interactions	23
1.2.2.4	Toxicology	24
1.2.3	Data from clinical studies	24
1.2.3.1	Clinical pharmacokinetics	25
1.2.3.2	Clinical Pharmacodynamics	

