Following the completion of three acceptable pre-bronchodilator forced expiratory manoeuvers, salbutamol (albuterol) will be administered to each subject. After a gentle and incomplete expiration, a dose of approximately 100 μ g of salbutamol (albuterol) is inhaled in one breath to total lung capacity. The breath is held for 5 – 10 sec before the subject exhales. Four separate doses (total dose approximately 400 μ g) are delivered at approximately 30 sec intervals (this dose ensures that the response is high on the salbutamol (albuterol) dose - response curve). Three to five additional, acceptable post-bronchodilator force expiratory manoeuver tests are recorded 15 – 30 minutes after the last dose of salbutamol (albuterol) is inhaled.

Boehringer Ingelheim		22 Apr 2021
BI Trial No.: 1405-0008		
c31693972-02	Clinical Trial Protocol	Page 61 of 111

During the study, a central quality control center will receive the data of spirometry measurements electronically to ensure that the sites maintain the same standard throughout the study. The central quality center will review the spirometry measurement data and report to the sponsor on data quality and, if required, actions to be taken.

Further instructions regarding FVC measurements will be provided in the ISF.

5.1.2 24h-sputum weight

Patients will be asked to collect spontaneous sputum into a pre-weighted container at home over 24 hours and seal it in the collection container on days before hand-over of 24 hour sputum is indicated in the Flow Chart. The collection of the sputum has to be done over the 24 hours preceeding the handover at the site. At the site the sputum weight will be determined. More details about the procedure will be provided in the ISF.

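### Cheap improvement: giving out the 24 h sputum container at V2b and V9b allows an incomplete baseline or week-12 collection when those visits run a day late or a sample is repeated

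*Protocol*

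**What the plan says.** Protocol section 5.1.2, listed under assessment of efficacy, describes the measure: "Patients will be asked to collect spontaneous sputum into a pre-weighted container at home over 24 hours". It fixes the period: "The collection of the sputum has to be done over the 24 hours preceeding the handover at the site". Further procedural detail is left to the investigator site file.

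Main Flow Chart footnote 8 fixes when the patient receives the container: "Sputum containers for 24h sputum collection will be provided to the patient at Visit 2b, Visit 5 and Visit 9b". These serve the handovers at V3, V6 and V10 respectively.

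The Main Flow Chart gives the visit days, "Day -27 -6 -2 1 8 15 29 43 57 78 82 84 98", and the windows, "Time window for visits (days) +14 +2 +1 ±0 ±3 ±3 ±3 ±3 ±3 +3 +1 +3 ±4". So V2b is day -2 (+1), V3 is day 1 (±0), V9b is day 82 (+1) and V10 is day 84 (+3). The Sample and Assessment Flow Chart gives +5 for V10.

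The Sample and Assessment Flow Chart gives the clock times:
- V3, 08:00: "Hand over of 24h sputum collected at home, safety, baseline PK and blood PD". Handover at V6 and V10 is also at 08:00.
- V2b, 09:00: "Sputum collection incl Murray chart and NEATstik", then pulmonary function at 11:00.
- V9b, 08:00: sputum collection only.

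Footnote 5 of that chart allows a 2 h timeframe for site sputum. For a sample that fails the quality criteria it says "re-sampling at the next day is generally possible". Footnote 1 accepts ±120 minutes around the clock times.

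**The concern.** A home collection cannot begin before the patient holds the container. If the dispensing visit falls on the calendar day before handover, the 24 h period is already due to start at 08:00 that morning, when the patient is at the site. The patient also coughs into the site sample for up to 2 h of that period. A repeat sample on the day before handover has the second effect even though the container was given out on time.

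Only the baseline and week-12 collections are exposed, because the week-4 container comes from V5. A site that keeps every visit date in window could therefore deliver a collection that is short at baseline, at week 12, at both or at neither, and part of the change in 24 h weight would reflect visit timing. The measure bears on a mechanism that the Protocol expects: section 1.1 anticipates less mucus hypersecretion, and section 1.4.1 names sputum volume as a possible benefit. The visible documents do not say how to treat an affected collection. SAP section 6.6.2 excludes values for late sputum processing and for restricted medication only.

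**Working it through.** The plan states no figure to reproduce. The check is of dates, hours, and what follows for the change from baseline.

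**1. Calendar gap between container and handover**

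| Pair | Planned | Range allowed |
|---|---|---|
| V9b to V10 | 84 - 82 = 2 days | shortest 84 - 83 = 1 day |
| V2b to V3, no day 0 | day -2 to day 1 = 2 days | shortest, day -1 to day 1 = 1 day |
| V2b to V3, with a day 0 | 3 days | shortest 2 days |
| V5 to V6 | 29 - 15 = 14 days | 26 - 18 = 8 to 32 - 12 = 20 days |

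For V9b and V10, one of 2 × 4 = 8 permitted date pairs has a one-day gap (one of 2 × 6 = 12 with the +5 window). These count date pairs and are not expected frequencies.

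**2. Is there a day 0?** The V9b part does not depend on this; the V2b part does.
- Against a day 0: SAP section 6.7 numbers days before first dose by simple date difference, so the day before day 1 is day -1. Protocol Figure 3.1: 1 runs to -1 and then to 1. Without a day 0 the two sputum blocks also match: V2a, V2b and V3 are spaced 4 and 2 days, as are V9a, V9b and V10 (78, 82, 84).
- For a day 0: the Main Flow Chart labels day -27 as week -4 and day -6 as week -1. These are exactly 28 and 7 days before day 1 only if a day 0 is counted.

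**3. Repeat samples.** A repeat after V9b on day 82 falls on day 83, the day before a day-84 V10. A repeat after V2b on day -2 falls on day -1, the day before V3 if there is no day 0. With a day 0, only a repeat after a late V2b falls on the day before V3. A repeat after V5 still leaves at least 8 - 1 = 7 days to V6.

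**4. Hours left when the gap is one day.** Hours = 24 + 8 - (clock time at which the container is received).
- V9b, after the 08:00 to 10:00 collection: 32 - 10 = 22 h, short by 2/24 = 8.3%.
- V2b, at 11:00 to 12:00 (0 to 1 h for spirometry is my assumption): 32 - 11 = 21 h to 32 - 12 = 20 h, short by 3/24 = 12.5% to 4/24 = 16.7%.
- Either visit, container given at 08:00: the full 24 h can elapse, but up to 2 h goes into the site sample (2/24 = 8.3% of the time).
- With ±2 h at both visits: 22 ± 4 = 18 to 26 h at V9b, and 20 - 4 = 16 to 21 + 4 = 25 h at V2b.

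**5. Effect on one patient's change**, assuming even output over the day and no true change:
- Short week 12, intact baseline: 22/24 - 1 = -8.3%.
- Short baseline, intact week 12: 24/21 - 1 = +14.3% to 24/20 - 1 = +20%.
- Both short: 22/21 - 1 = +4.8% to 22/20 - 1 = +10%.

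**6. Effect on a small group.** SAP section 6.1 analyses placebo by trial part, which gives 12/4 = 3 patients in Part A and 24/4 = 6 in Part B. In the group of three, one affected patient moves the mean percent change by 8.3/3 = 2.8 points (week 12 short) or up to 20/3 = 6.7 points (baseline short).

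**The case against.** The case on the other side is substantial, and most of it limits the point.

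- A reader might infer that baseline and week-12 collections will usually be short. The documents do not support that. On planned days without re-sampling a full 24 h fits at both visits; the clash needs the late edge of a window or a repeat sample.
- A reader might infer a loss of up to 17% at week 12 as well. At planned clock times that figure belongs to V2b, where spirometry follows at 11:00. V9b has no spirometry and the loss there is about 2 h, or 8%.
- A reader might infer a biased treatment comparison. Patients and sites are blinded (Protocol section 4.1.5.1) and the schedule is the same for all arms, so the error should not differ systematically by arm. What remains is noise, which can move a very small group in either direction.
- Section 5.1.2 already states the 24 h requirement, so a site that delivers 20 h departs from it. That is true, but on these dates footnote 8 makes the requirement hard to meet.
- The site file may contain a further instruction, and Main Flow Chart footnote 7, attached to site sputum, is blank in the public text. It can therefore be said only that no visible text resolves the clash.
- 24 h sputum weight is not among the listed primary or secondary endpoints, and text on further endpoints and their analysis is not visible.

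**Conclusion.** The point holds as a conditional scheduling clash that is cheap to remove. The firmest part is V9b on day 83 with V10 on day 84: about 22 h remain, 8% short at planned clock times. The corresponding V2b case, at 20 to 21 h or 12.5 to 17% short, holds only if there is no day 0. The balance of the documents favours that, but the week labels do not. A repeat sample on the day before handover diverts up to 2 h of sputum without delaying the start; for V2b this again assumes no day 0 when the visit itself was on time. Week 4 is clear.

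The percentages are shares of time. They equal shares of weight only if output is even over the day, and assisted expectoration at the site could make the lost weight larger. The consequence is mainly added variability in one supporting efficacy assessment. It does not touch the primary endpoint or the listed secondary endpoints.

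**What to change.** Change footnote 8 so that the containers are dispensed at V2a, V5 and V9a. The latest V2a (day -6 + 2 = day -4) is at least 4 days before V3, and the latest V9a (day 78 + 3 = day 81) is at least 3 days before V10. The container would then always be in hand before the 24 h period starts.

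Keep the +1 windows and next-day re-sampling at V2b and V9b. Removing them would cost more than it gains: V2b carries the NEATstik eligibility criterion and its re-test, and both visits supply samples for the sputum NE secondary endpoint. Where a site sputum collection falls inside the 24 h before handover, record its time and weight, and flag that 24 h weight as incomplete in any change-from-baseline summary.

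State whether day numbering includes a day 0, and reconcile the V10 window between the two flow charts (+3 and +5).

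The cost is one footnote, one flag and the weighing of the affected site samples. A few containers will go to patients who then fail at V2a or V2b; handing them out after the V2a NEATstik result limits this. A few 24 h weights will be flagged.
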